6.3 Schedule of Analyses

Primary analyses will compare the two randomised arms in an intention to treat manner once all patients have completed follow up (week 18). Secondary analyses will exclude data in patients who cease study drug. There will be no adjustment of analyses for multiple comparisons.

7.0 Participant population

Eligible participants will satisfy all the following inclusion and exclusion criteria within 14 days prior to randomisation. No waivers will be issued.

7.1 Eligibility criteria

Inclusion criteria

1. HIV-1 positive by licensed diagnostic test
2. aged ≥ 40 years
3. plasma HIV RNA < 50 copies/mL for at least 24 weeks
4. screening CD4+ cell count > 50 cells/mm³
5. treated for at least 12 weeks with a suppressive regimen of combination antiretroviral therapy that does not include HIV protease inhibitors and/or NNRTIs (except rilpivirine)
6. plasma d-dimer > 200 ng/mL mL (> 0.2 µg/mL or > 0.2 mg/L) fibrinogen equivalent units or > 100 ng/mL (> 0.1 µg/mL or > 0.1 mg/L) d-dimer units in the absence of established cause (deep vein thrombosis/embolism)
7. provision of written informed consent

Exclusion criteria

1. Absolute neutrophil count (ANC) < 1000 cells/µL
2. haemoglobin < 10.0 g/dL
3. platelet count $< 75,000$ cells/µL
4. AST and/or ALT > 2.5 x ULN
5. estimated glomerular filtration rate < 30 mL/min/1.73m²) using CKD-EPI (Chronic Kidney Disease Epidemiology Collaboration) equation
6. history of myocardial infarction or unstable atherosclerotic disease
7. history of ischemic stroke or transient ischaemic attack (TIA)
8. active peptic/duodenal ulcer or other bleeding disorder within the previous 12 months

9. intent to have surgery within the 6 month period after randomisation
10. current use of aspirin or P2Y12 antiplatelet therapy
11. current use of anticoagulants, (e.g. heparin or warfarin), fibrinolytic therapy, chronic (more than 5 consecutive days) nonsteroidal anti-inflammatory drugs (NSAIDs), strong CYP3A4 inhibitors or inducers. See Manual of Operations for full list of medications to avoid.
12. participants unlikely to be able to remain in follow-up
13. pregnant or nursing mothers
14. in the clinical judgement of the investigator, participation in this trial is deemed inappropriate as this may conflict with the well-being of the participant

8.0 Treatment of participants

Eligible participants will be randomised in equal proportions to receive either:

- I. vorapaxar sulphate (2.5mg qd) for 12 weeks
- II. matched placebo for 12 weeks

All participants will stop study treatment at the week 12 visit and then be seen for a final visit at week 18. All participants will stop taking the study medication at the week 12 visit, even if having undergone a period of study drug interruption. The treatment period will not be extended to account for the missing days.

Randomisation will be conducted via the electronic case report form. Specific details regarding randomisation will be provided in the study Manual of Operations (MOOP). Randomisation will be stratified by centre on a 1:1 basis.

8.1 Vorapaxar

Vorapaxar sulphate is an oral competitive PAR-1 antagonist that inhibits thrombin-induced platelet aggregation. Vorapaxar is eliminated primarily by metabolism with contributions from CYP3A4 and CYP2J2. The primary route of elimination is through the faeces and to a lesser degree in urine. It has an effective half-life of 3-4 days and an apparent terminal elimination half-life of 8 days (range 5-13 days).

One vorapaxar sulphate encapsulated tablet (2.5mg) or matching placebo should be taken orally, once daily with or without food. A one month supply of vorapaxar or matching placebo will be provided at each dispensing visit (weeks 0, 4 and 8). Study drug will be dispensed from local pharmacies in a bottle containing a desiccant packet to protect the drug from moisture. The bottles must be stored at 20-25°C (68-77°F). Temperature monitoring logs will be kept at each pharmacy and checked during monitoring visits. All details regarding supply and dispensing of study treatment will be outlined in the MOOP.

8.2 Prior and concomitant medications

Given the involvement of CYP3A4 and CYP2J2 in the metabolism of vorapaxar, participants with HIV infection whose ART therapy includes ritonavir or cobicistat boosted PIs or NNRTIs (apart from rilpivirine) will not be enrolled into the study. Vorapaxar can increase the risk of bleeding in proportion to a participant's underlying bleeding risk. To this end, participants who have a history of bleeding disorders, active bleeding or are planning to undergo an elective surgical procedure within the 6 month period following randomisation will be excluded from the study. Certain concomitant medications are also known to increase the risk of

bleeding. As such, participants taking anticoagulants, (e.g. heparin or warfarin), fibrinolytic therapy or chronic (more than 5 consecutive days) nonsteroidal anti-inflammatory drugs (NSAIDS) will also be excluded from the study. A list of medications to avoid will be listed in the MOOP.

If during the course of the study, a participant needs treatment with a potent CYP3A4 inhibitor or inducer or other medication listed above, study treatment must be discontinued immediately. In the case of a potent CYP3A4 inhibitor or inducer, where possible, an alternative treatment should be given to avoid participants coming off study medication unnecessarily. Study treatment should recommence as soon as clinically possible with the safety and well-being of the participant paramount. It is important that the treating physician is informed that vorapaxar results in residual platelet aggregation activity 4 weeks after stopping and appropriate clinical decisions are made. Whilst there is no known antidote for vorapaxar, monkey data suggest that platelet transfusions of sufficient quantity (a full pheresis pack or two) have the potential to transiently (a few hours) reverse the antiplatelet activity of vorapaxar. It is the investigator's responsibility to inform the treating physician of this.

In this protocol all concomitant medications including over the counter medicines and natural supplements will be recorded.

8.3 ART Regimen

Participants will continue to have their ART regimen managed as directed by their treating physician in accordance with national and international guidelines. Modifications to the ART regimen can be made if required. However, ritonavir boosted PIs, elvitegravir+cobicistat (Stribild™ Genvoya™) or NNRTIs (apart from rilpivirine), should not be prescribed as they are potent inhibitors or inducers of CYP3A4. Rilpivirine is permitted as it is not a potent CYP3A4 inducer. At the recommended dose of 25mg daily, rilpivirine is not expected to have a clinically significant effect on vorapaxar exposure. Similarly, maraviroc is not expected to have a clinically significant effect on vorapaxar exposure as it does not inhibit any of the major CYP isoforms. Conversely vorapaxar is not expected to have a clinically significant effect on rilpivirine or maraviroc.

Warnings and precautions regarding medications to avoid whilst taking vorapaxar can be found in the FDA approved product information and Investigator Brochure. For ART medications Investigators can refer to the respective product information or www.HIV-druginteractions.org.

Participants will receive their ART medication in the usual manner and this will not be provided by the study.

9.0 Study procedures

9.1 Initial screening period

Potentially eligible individuals can be screened within 14 days before the randomisation visit and all results from screening must be available for randomisation. All subjects should be given adequate information about the trial including the Participant Information Sheet and be given an opportunity to ask questions about the trial. Written consent for the trial should be obtained at the screening visit before any protocol specified assessments are performed. The following evaluations will be performed within 14 days prior to randomisation:

9.1.1 Clinical assessments at screening

- Informed consent
- Complete medical history to include; non-HIV related diagnosis including liver disease, renal disease, cardiovascular disease, bleeding disorders, race and gender at birth, surgical history and concomitant medications
- Full HIV history to include: mode of transmission, duration of HIV infection, ART history and current ART regimen, current stage of HIV disease (CDC classification – refer Appendix 3)
- Symptom directed physical examination

9.1.2 Laboratory assessments at screening

- If the patient is female and is of child bearing potential, she must have a urine or blood sample pregnancy test
- Serum chemistries and liver function tests: electrolytes (sodium, potassium, bicarbonate, chloride, phosphate), urea, creatinine and LFTs (ALT and AST only)
- Assessment of renal function will be undertaken with derivation of creatinine clearance using the CKD-EPI (Chronic Kidney Disease Epidemiology Collaboration) equation:

Estimated GFR = $141 \times \min(\text{SCR}/\kappa, 1)^\alpha \times \max(\text{SCR}/\kappa, 1)^{-1.209} \times 0.993^{\text{Age}^e} \times (1.018 \text{ if female} \times (1.159 \text{ if black}))$

- Haematology: full blood count (haemoglobin, white cells, neutrophils, lymphocytes, platelets)
- Plasma HIV-RNA analysis
- Immunology: CD4 and CD8 (% and absolute)
- Plasma d-dimer

9.1.3 Rescreening

Rescreening is not permitted, including those participants with abnormal laboratory results. All screen failures must be documented on the site screening and randomisation log.

9.2 Randomisation visit

To proceed to the randomisation visit, all participants must have fulfilled the eligibility criteria by the results of evaluations at screening. All randomisation evaluations must be completed prior to the commencement of study drug

9.2.1 Clinical assessments at week 0 (prior to randomisation)

- Targeted physical examination (symptom directed). Symptoms reported by the subject will be reviewed by the clinician at each visit and recorded on the CRFs as adverse events
- Vital Signs: height, weight and sitting blood pressure
- Information required for Framingham risk¹⁷ equation (smoking and diabetes)
- Concomitant medication information

9.2.2 Laboratory assessments at week 0 (prior to randomisation)

- If the patient is female and is of child bearing potential, she must have a urine or blood sample pregnancy test
- Serum chemistries and liver function tests: electrolytes (sodium, potassium, bicarbonate, chloride, phosphate), urea, creatinine and LFTs (ALT and AST only)
- Haematology: full blood count (haemoglobin, white cells, neutrophils, lymphocytes, platelets)
- Fasted lipids
- Plasma HIV-RNA levels
- Immunology: CD4 and CD8 (% and absolute)
- PAR-1 (to be analysed in a subset of participants from selected sites with capacity to perform this assay in real time)
- Plasma storage for central laboratory testing of d-dimer, Hs-CRP, IL-6
- Plasma, PBMC and serum storage for possible exploratory analysis of ultra-sensitive plasma viral load, T cell activation, NK cell function, ADCC antibody and markers of inflammation (sCD14, sCD163)

9.2.3 Randomisation and Drug Supply

After completion of all randomisation study visit assessments the participant will be randomised online via the web based CRF. Eligibility must be confirmed and the participant will then be automatically randomised to commence either vorapaxar sulphate (2.5mg) or matching placebo once daily. A Participant Identification (PID) number will be provided.

The treatment assignment will be stratified according to clinical site.

The investigator should complete a prescription and the participant should fill the prescription that same day or the next. Therefore, the study drug should be commenced within 1 day of randomisation.

9.3 Follow Up Visits

The scheduled date of study visits will be calculated from the date of randomisation (day 0, week 0). A schedule of the dates for study visits will be provided for each participant, once randomisation has been completed. Guidance for site staff will also be detailed in the MOOP.

The window period for each study visit is continuous so that all data collected may be used. The window period for: week 1 is between day 1 and day 13 from randomisation (inclusive); week 4, 8 and 12 visits in each treatment phase should be conducted 2 weeks before or after the scheduled visit date. Week 18 to be conducted no later than 2 weeks after the scheduled visit date.

9.3.1 Clinical assessments at weeks 1, 4, 8, 12, 18

- Targeted physical examination (symptom directed) [weeks 1, 4, 8, 12, 18]
- Symptoms reported by the subject or symptoms identified after examination will be reviewed by the clinician at each visit and recorded on the CRFs as adverse events [weeks 1, 4, 8, 12, 18]
- Updated medical history including changes or additions to diagnoses, diseases, or any change in antiretroviral drugs, prescribed concomitant medications [weeks 1, 4, 8, 12, 18]
- Sitting blood pressure [weeks 1, 4, 8, 12, 18]
- Weight [week 18 only]
- Dispense study medication [weeks 4 and 8 only]

9.3.2 Laboratory assessments at weeks 1, 4, 8, 12, 18

- If the participant is female and is of child bearing potential, she must have a urine or blood sample pregnancy test [weeks 4, 8, 12, 18]
- Haematology: full blood count (haemoglobin, white cells, neutrophils, lymphocytes, platelets) [weeks 1, 4, 8, 12, 18]
- Blood sample for haemoglobin measurement to be taken if the participant experiences a clinically significant bleeding event (clinical judgement to be used)
- Plasma HIV-RNA levels [weeks 1, 4, 8, 12, 18]
- Immunology: CD4 and CD8 (% and absolute) [weeks 1, 4, 8, 12, 18]
- Serum chemistries and liver function tests: electrolytes (sodium, potassium, bicarbonate, chloride, phosphate), urea, creatinine and LFTs (ALT and AST only) [weeks 12 and 18 only]
- PAR-1 (to be analysed in a subset of participants from selected sites with capacity to perform this assay in real time) [weeks 1, 4, 12, 18]
- Plasma storage for central laboratory testing of d-dimer, Hs-CRP, IL-6 [weeks 1, 4, 8, 12, 18]
- Plasma, PBMC and serum storage for possible exploratory analysis of T cell activation, NK cell function and ADCC antibody [weeks 1, 4, 8, 12, 18]
- Plasma storage for possible exploratory analysis of markers of inflammation (sCD14, sCD163) and ultra-sensitive plasma viral load [weeks 12 and 18 only]

9.4 Missed visits and missed assessments

All efforts should be made to schedule visits in keeping with the proposed week numbers and to carry out all required assessments at these visits. Any missed study visits or missed assessments should be indicated as such on the eCRF. If a scheduled visit is conducted after the window period has ceased for that specific visit, it will be counted as the next visit, and the previous visit should be documented as “missed”. DO NOT conduct a second routine visit in the same window period.

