2.0 Study Flow Chart: Time and events schedule

Study Phase	Screening	Randomisation	Phase 1				Phase 2	
Study week number ^c	SCRN ^a	0 ^b	1	4	8	12	13-17 No study drug	18
Clinical Assessments								
Informed consent	•							
Medical and HIV history	•							
Interim history, AEs assessment and concomitant medication		•	•	•	•	•		•
Targeted physical examination (symptom directed)	•	•	•	•	•	•		•
Vital Signs ^d		•	•	•	•	•		•
Dispense study medication		•		•	•			
Real time local laboratory assessments								
Biochemistry ^e	•	•				•		•
Liver function ^f	•	•				•		•
Haematology ^g	•	•	•	•	•	•		•
Fasted lipids ^h		•						
CD4+ and CD8+ T cell (absolute and %) ⁱ	•	•	•	•	•	•		•
Virology: plasma HIV-1 RNA ^j	•	•	•	•	•	•		•
d-dimer	•							
Pregnancy test ^k	•	•		•	•	•		•
Storage samples for central laboratory analysis								
D-dimer		•	•	•	•	•		•
Hs-CRP		•	•	•	•	•		•
IL-6		•	•	•	•	•		•
Storage samples for central laboratory analysis (exploratory analysis)								
Ultrasensitive plasma viral load		•				•		•
T cell activation marker		•	•	•	•	•		•
ADCC Antibody/ NK cell function		•	•	•	•	•		•
PAR-1 expression ^l		•	•			•		•
Plasma markers of inflammation (sCD14, sCD163)		•				•		•

a All screening assessments are to be completed within 14 days prior to randomisation;

b All randomisation (week 0) assessments should be completed before the participant commences study drugs. Study drug should commence within 1 day of randomisation;

c Study Week Number: All efforts should be made to schedule visits in keeping with the proposed week numbers. Phase 1: week 1 to be conducted within 13 days of randomisation, weeks 4, 8 and 12 to be done +/- 2 weeks of scheduled visit date. Phase 2: week 18 to be conducted within + 2 weeks of scheduled visit date.

d Vital Signs: Sitting blood pressure (all visits), height (week 0 only) and weight (week 0 and week 18 only);

e Biochemistry: electrolytes (sodium, potassium, calcium, bicarbonate, chloride, phosphate), creatinine, urea;

f Liver Function test: ALT and AST;

g Haematology: haemoglobin, white blood cells, neutrophils, lymphocytes, platelets to be done (day 0 and week 12 to be done as standard of care). Haemoglobin to be tested at the time of any clinically significant bleeding event (clinical judgement to be used);

h Fasting lipid parameters includes: total cholesterol, HDL cholesterol, calculated LDL cholesterol and triglycerides;

i CD4+ and CD8+ cell counts: Day 0 and week 12 to be done as standard of care;

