6.0 Study design & Statistics

This is an international, multi-centre, double-blind, placebo controlled trial. Randomisation will be stratified by clinical site.

Consenting participants will be screened and within 14 days randomly allocated to receive either vorapaxar sulphate (2.5mg qd) or matched placebo once daily for 12 weeks (phase 1). At the week 12 visit, all study treatment will stop for 6 weeks (phase 2). Patients will be seen for a final visit at week 18.

The study designed is summarised in Figure 1.

[figure not shown]

Figure 1. Study Design

60 participants will be randomised from approximately 7 selected centres in Australia and the USA and followed for a total of 18 weeks. It is anticipated that approximately 120 patients will need to be screened to randomise 60 participants. It is expected that the majority of ineligible participants through screening will be those with low d-dimer levels.

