12.2 Handling and dispensing of study drugs

Study drugs must only be dispensed according to the protocol and MOOP. It is the responsibility of the Investigator to ensure that study drug is only dispensed to study participants and only dispensed by suitably trained, authorised personnel according to local regulations at recognised hospital and clinic pharmacies.

Study drugs should only be dispensed on receipt of a prescription written by the Principal Investigator or designee at the site. This prescription must contain the unique participant identification number.

The participant must be instructed to take the study drug tablets whole and to store all medication safely out of sight and reach of children.

Once the participant has been randomised, a one month blinded supply of vorapaxar or placebo will be dispensed to the participant from clinical supplies stored at the study site. At each subsequent visit, participants will be required to return empty, partially used and unused study drug containers that will be retained at the site for later destruction at the approval of the Sponsor. Records must be kept of unreturned study drug and/or containers. No drugs will be returned to the Sponsor.

At each dispensing, participants should be counselled on adherence issues. All participants should be counselled regularly on the need for maintaining strict adherence with the allocated study regimens. The objective should be 100% adherence at all times during follow-up. The site Principal Investigator is responsible for assessing adherence with all aspects of the study including use of study drugs and attendance at protocol-mandated clinical visits and assessments.

The Investigator must be satisfied that the participant has returned or accounted for all unused study drug before additional medication is dispensed. If the number of encapsulated tablets recorded as used is substantially different from the number prescribed, the participant must be counselled on how study drugs should be taken. If such deviations persist, the Investigator may consider discontinuing the regimen for non-adherence. If this occurs, the participant must remain in follow-up and undergo the protocol-specified assessments and evaluations.

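### A week-12 visit held after day 98 is counted as the 6-week off-drug week-18 visit, and the SAP has no date rule to undo this; the effect is minor and limited to the week-18 endpoints

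*Protocol*

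**What the plan says.** Protocol section 9.3 counts visit dates from randomisation (day 0) and allows weeks 4, 8 and 12 a margin of two weeks either side. Section 9.4 then deals with lateness: "If a scheduled visit is conducted after the window period has ceased for that specific visit, it will be counted as the next visit". Whichever visit was due is then recorded as missed. The same section forbids two routine visits in one window. It makes no exception where treatment ends.

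The week-12 visit is where treatment ends. Section 6.0 says: "At the week 12 visit, all study treatment will stop for 6 weeks (phase 2". The flow chart in section 2.0 heads the interval "13-17 No study drug". The secondary objective (section 5.2) is a rise in d-dimer over 6 weeks after cessation.

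The limits of the week-18 window come in three statements:

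- Flow chart, footnote c: "Phase 2: week 18 to be conducted within + 2 weeks of scheduled visit date".
- Section 9.3: "Week 18 to be conducted no later than 2 weeks after the scheduled visit date".
- Section 9.3, for all visits: "The window period for each study visit is continuous so that all data collected may be used".

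The SAP defines the primary endpoint on the average of weeks 8 and 12 (section 4.1) and a set of week-18 endpoints (section 4.2). It summarises by study visit (section 4.3) and uses all available follow-up data (section 1.3). It gives no analysis windows and no rule for assigning a sample by date.

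**The concern.** Relabelling a late week-4 visit as week 8 keeps the sample within the treatment phase. Relabelling a late week-12 visit as week 18 moves it into a different phase: a sample taken as treatment ends, or shortly after, is filed as the measurement made 6 weeks later. If some drug effect is still present, that sample understates the off-drug rise in d-dimer, and it enters every week-18 endpoint in the SAP.

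The participant's proper week-18 sample may also be affected. Depending on when the window opens, that visit is either barred as a second visit in the same window or allowed but left competing with the earlier record for the same label.

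**Working it through.** **The plan's own power figure.** Inputs from protocol section 6.1: SD 0.4, correlation 0.5, 28 per arm, difference 0.26; two-sided 0.05 from section 6.2.1.

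- Variance of the two-visit mean = 0.16 × 1.5 / 2 = 0.12, so SD = 0.3464.
- SE of the arm difference = 0.3464 × √(2/28) = 0.0926.
- By the normal approximation, power is 80.2% at 0.26 and 90.0% at 0.30. The stated 80% (90%) is reproduced.

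**Windows.** Week 12 is day 84 ± 14, i.e. days 70–98. Week 18 is scheduled on day 126 and closes on day 126 + 14 = 140. The continuous-window sentence implies that it opens on day 99. The flow-chart footnote, read literally, implies day 126, which leaves days 99–125 (27 days) in no window. Section 9.4 labels a day-99 visit week 18 on either reading.

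**Days off drug.** Section 8.1 supplies one month at weeks 0, 4 and 8, taken here as 28–31 days (assumption). Section 12.2 has containers returned at each visit, so only the week-8 supply counts. Full adherence is assumed. Last dose = dispensing day + supply − 1. The week-8 window is days 42–70.

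| Week-8 dispensing | Last dose (day) | Off drug at day 99 | At day 112 | At day 125 |
|---|---|---|---|---|
| Day 42 | 69–72 | 27–30 | 40–43 | 53–56 |
| Day 56 | 83–86 | 13–16 | 26–29 | 39–42 |
| Day 70 | 97–100, cut at the visit | 0–2 | 12–15 | 25–28 |

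At day 99 every row falls short of 42 days. With dispensing on day 56 the gap has closed by about day 125. A correctly timed sample remains attainable for that participant: days 126–140 are 40–57 days off drug.

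**Drug remaining at 13–16 days**, as 2^(−t/half-life), with the half-lives in section 8.1:

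- Terminal, 8 days: 32–25%. Over the stated range of 5–13 days: 11–50%.
- Effective, 3–4 days: 2–11%.
- For comparison, at 42 days with 8 days: 2.6% (0.3–10.7% over 5–13 days).

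The share of drug remaining is not the share of d-dimer effect remaining. These figures show only that the samples differ in exposure.

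**Shift in the week-18 arm difference.** SE = 0.4 × √(2/28) = 0.107, with SD 0.4 assumed to hold at week 18. Shift = 0.26 × f × p, where p is the share affected and f the share of effect retained. Correctly timed samples are taken to retain no effect.

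| p (assumed) | Shift, f = 0.25–0.32 (assumed) | In SE units |
|---|---|---|
| 5% | 0.003–0.004 | 0.03–0.04 |
| 10% | 0.007–0.008 | 0.06–0.08 |
| 20% | 0.013–0.017 | 0.12–0.16 |

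**Primary endpoint.** An affected participant contributes week 8 only, with variance 0.16 instead of 0.12. Information per arm = 28(1 − p)/0.12 + 28p/0.16, and SE = √(2/information). For p = 5%, 10% and 20% the SE is 0.0932, 0.0938 and 0.0950, and power is 79.7%, 79.2% and 78.1%.

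**The case against.** **The window may be clearer than it looks.** The flow chart contrasts a two-sided margin for weeks 4, 8 and 12 with a plus-only margin for week 18, which points to days 126–140. A reader might infer that the late-visit rule always destroys the true week-18 sample. The documents do not support that: on the day-126 reading the proper visit is allowed, and only the day-99 reading bars it. What stands is that the statements conflict, and that on the day-126 reading two records may carry the same label with no rule to choose between them.

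**Day 98 is not a switch from on drug to off drug.** This is correct. After day-56 dispensing, an in-window visit on day 98 is already 12–15 days off drug. A participant who stops on day 98 and is seen on day 126 is only 28 days off drug. Part of the spread therefore comes from ordinary windows and supply length. The late-visit rule adds to it by filing an end-of-treatment visit as the off-drug visit.

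**It may be rare, and the Manual of Operations may cover it.** The documents give no count of visits after day 98, and it could be zero. The SAP's remark that follow-up was very good is made to explain why analyses for participants who stopped follow-up or drug seemed unnecessary. It does not address punctuality. Section 9.3 refers to site guidance in the Manual, which is not part of these documents; the protocol's own explicit rule is the one quoted.

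**The effect could be larger or smaller.** Full retention in 20% of participants would give 0.26 × 1 × 0.20 = 0.052, or 0.49 SE, but that stacks two unfavourable assumptions. If retention followed the effective half-life (at most about 10.5%), 20% affected would give 0.26 × 0.105 × 0.20 = 0.0055, or 0.05 SE. Sections 8.2 and 10.3.2.4 mention residual activity on platelet aggregation 4 weeks after stopping. That is not a d-dimer effect, but it is a reason not to treat early and 6-week samples as equivalent.

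**Conclusion.** Wrong as written, minor, and confined to the secondary off-drug endpoints. Followed literally, section 9.4 files an end-of-treatment visit held just after day 98 as week 18. The sample is then well short of 6 weeks off drug, and the SAP has no step that would move it back. The error tends to understate the off-drug rise. It is largest just after day 98 and fades as the visit gets later.

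Under the stated assumptions (5–20% affected, 25–32% of a 0.26 log10 effect retained, SD 0.4 at week 18) the arm difference shifts by about 0.03–0.16 SE. Neither the share affected nor the retained effect is given in the documents.

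A reader might also infer that the primary comparison is biased. It is not, directionally: both blinded arms follow the same rule and week 8 still contributes. The cost there is about 2 points of power at an assumed 20% affected. Since the missing week-12 value comes from lateness as well as from the rule, it is not counted as a separate harm.

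**What to change.** 1. **Section 9.4:** state that an end-of-treatment visit held after the week-12 window is not labelled week 18 and neither replaces nor bars the week-18 visit.
2. **Flow chart, sections 9.3 and 9.4:** reconcile them to one week-18 window with a stated lower limit.
3. **SAP:** assign samples to week 12 or week 18 from visit dates and last-dose dates, and exclude late end-of-treatment samples from the week-18 endpoints. Prespecify whether those samples enter the week 8/12 average, with the alternative as a sensitivity analysis. Either choice is arguable. Leaving them out runs against the aim in section 9.3 of using all data. Including them gains power only if about 75% or more of the effect remains: with 10% affected, power is 79.2% if they are left out and 77.1% if they are included at 25% retention (effect 0.26 × (1 − 0.10 × 0.75/2) = 0.250, SE 0.0926).
4. **SAP:** report days off drug at week 18 by arm, with a sensitivity analysis restricted by that interval. It should remain a sensitivity analysis because the interval is a post-randomisation variable.

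The cost is wording changes and two short sensitivity analyses on visit and last-dose dates. Late attenders still come to the week-18 visit that is already planned. If visits are already complete, items 3 and 4 are the parts that can still be acted on.
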